4.5.6 Oxygen treatment, ventilator use and mSOFA

[figure not shown]
Oxygen treatment and ventilator use data will be used to assess efficacy endpoints of the study.

The number and percentage of subjects requiring oxygen treatment or mechanical ventilation at each timepoint will be presented. The method of oxygen or mechanical ventilation, as well as the number and percentage of subjects who go from oxygen treatment to mechanical ventilation, will also be summarized.

For subjects requiring oxygen treatment, by-subject listings will be presented.

For subjects requiring mechanical ventilation, by-subject listings will be presented on the data collected, as listed in Section 3.2.6.

By-subject listings of mSOFA scores and sub-scores may be presented.

5. INTERIM ANALYSES

There are no formal interim futility and interim efficacy analyses in this study.

6. INDEPENDENT DATA MONITORING COMMITTEE

This study will not have iDMC.

7. SAFETY REVIEW COMMITTEE

This study will have an SRC. The SRC will conduct scheduled reviews of safety and other relevant data. In addition, The SRC will meet to review any of the following events should they occur during the study:

- Any death due to acalabrutinib (per Investigator)
- Any Grade 4 hemorrhage due to acalabrutinib (per Investigator)

The SRC will consist of the AstraZeneca Study Physician or delegate, Principal Investigator or equivalent delegate from active investigational sites, and Global Safety Physician or delegate. Other attendees may also be invited as appropriate.

Details on the process of ongoing evaluation of safety data by the SRC and the committee composition is described further in the SRC charter.

8. CHANGES OF ANALYSIS FROM PROTOCOL

N/A

9. APPENDIX

9.1 **AESI and ECI definitions**

Adverse Event of Special Interest (AESI)

The following preferred terms for the ventricular arrhythmias AESI include:

- Torsade de pointes
- Ventricular arrhythmia
- Ventricular extrasystoles
- Ventricular fibrillation
- Ventricular flutter
- Ventricular tachyarrhythmia
- Ventricular tachycardia
- Suspected transmission of an infectious agent via product

Events of Clinical Interest

The Events of Clinical Interest (ECIs) have been identified based on preclinical findings, emerging data from clinical studies relating to acalabrutinib, and

The adverse events (AEs) selected for

dedicated analysis were evaluated using Standardized MedDRA Queries (SMQs), where available, by System Organ Classes (SOCs), or by Sponsor-defined baskets of MedDRA Adverse Event Grouped Terms.

Category	Subcategory	Definition
Cardiac events		 SOC Cardiac disorders
	Atrial fibrillation	PT Atrial fibrillation
		PT Atrial flutter
	Ventricular	 PT Torsade de pointes
	tachyarrhythmias	PT Ventricular fibrillation
		 PT Ventricular flutter
		 PT Ventricular tachyarrhythmia
		PT Ventricular tachycardia
Cytopenias –		 SMQ Haematopoietic erythropenia [narrow +
Anemia		broad]
Cytopenias –		 SMQ Haematopoietic leukopenia [narrow +
Leukopenia		broad]
	Neutropenia	 PT Band Neutrophil count decreased
		 PT Band neutrophil percentage decreased
		 PT Cyclic neutropenia
		 PT Febrile Neutropenia
		 PT Idiopathic neutropenia
		 PT Neutropenia
		 PT Neutropenic infection

		PT Neutropenic sepsis
		 PT Neutrophil count decreased
		 PT Neutrophil percentage decreased
	Other leukopenia	SMQ Haematopoietic leukopenia [narrow + broad] excluding PTs for neutropenia above
Cytopenias - Thrombocytopenia		• SMQ Haematopoietic thrombocytopenia [narrow + broad]
Hemorrhage		SMQ Haemorrhage terms (excl laboratory terms)
	Major hemorrhage	As per Acerta definition (see below)
Hepatotoxicity		 SMQ [narrow] Hepatic failure, fibrosis and cirrhosis and other liver damage-related conditions
		 SMQ [narrow] Hepatitis, non-infectious
		• SMQ [narrow] Liver related investigations signs
Hypertension		 SMQ Hypertension [narrow]
Infections		 SOC Infections and infestations
Interstitial lung disease/Pneumonitis		SMQ [narrow] Interstitial lung disease
Second primary malignancies		 SMQ Malignant tumours (including Haematological malignant tumours SMQ and Non-haemoatological malignant tumours SMQ) SMQ Malignant lymphomas [narrow] SMQ Myelodysplastic syndrome [narrow]
	Second primary malignancies (excluding non melanoma skin)	The above excluding PTs mapping to HLT Skin neoplasms malignant and unspecified (excluding melanoma)
Tumor lysis syndrome		PT Tumour lysis syndrome

MedDRA version 23.0

HLT=High-Level Term; PT=Preferred Term; SOC=System Organ Classes; SMQ=Standardized MedDRA Queries.

Major Hemorrhage

Major hemorrhage is defined as any hemorrhagic event that is serious, or Grade ≥ 3 in severity, or that is a CNS hemorrhage (any severity grade).

Search Strategy:

- I. Use standardized MedDRA version 23.0 query:
 - o Haemorrhage terms (excluding laboratory terms) (SMQ) [20000039]
- II. Identify Major Events that are a subset of the Haemorrhage SMQ:
 - \circ Grade ≥ 3 AE
 - o Any serious adverse event
 - o All grades of CNS hemorrhage

CNS Hemorrhage Preferred Terms (MedDRA Version 23.0)

- Acute haemorrhagic leukoencephalitis
- Basal ganglia haematoma
- Basal ganglia haemorrhage
- Basilar artery perforation
- Brain contusion
- Brain stem haematoma
- Brain stem haemorrhage
- Brain stem microhaemorrhage
- Central nervous system haemorrhage
- Cerebellar haematoma
- Cerebellar haemorrhage
- Cerebellar microhaemorrhage
- Cerebral aneurysm perforation
- Cerebral aneurysm ruptured syphilitic
- Cerebral arteriovenous malformation haemorrhagic
- Cerebral artery perforation
- Cerebral cyst haemorrhage
- Cerebral haematoma
- Cerebral haemorrhage
- Cerebral haemorrhage foetal
- Cerebral microhaemorrhage
- Encephalitis haemorrhagic
- Epidural haemorrhage
- Extradural haematoma
- Haemorrhage intracranial
- Haemorrhagic cerebral infarction
- Haemorrhagic stroke
- Haemorrhagic transformation stroke
- Intracerebral haematoma evacuation
- Intracranial haematoma
- Intracranial tumour haemorrhage
- Intraventricular haemorrhage
- Meningorrhagia
- Ocular retrobulbar haemorrhage
- Optic disc haemorrhage
- Optic nerve sheath haemorrhage
- Pituitary haemorrhage
- Putamen haemorrhage
- Retinal aneurysm rupture
- Retinal haemorrhage
- Retinopathy haemorrhagic
- Ruptured cerebral aneurysm
- Spinal cord haematoma
- Spinal cord haemorrhage

- Spinal epidural haematoma
- Spinal epidural haemorrhage
- Spinal subarachnoid haemorrhage
- Spinal subdural haematoma
- Spinal subdural haemorrhage
- Subarachnoid haematoma
- Subarachnoid haemorrhage
- Subdural haematoma
- Subdural haematoma evacuation
- Subdural haemorrhage
- Subgaleal haematoma
- Subgaleal haemorrhage
- Subretinal haematoma
- Thalamus haemorrhage
- Traumatic intracranial haematoma
- Traumatic intracranial haemorrhage

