A listing of all AEs (including non-treatment-emergent events), by E-code, AE (SOC, PT, verbatim term), date of onset, date of resolution, duration, CTCAE grade, seriousness, action taken, outcome, relationship to study treatment and time from last dose to start of AE.

4.5.1.1 Deaths, serious adverse events (SAEs), and other significant adverse events The following summaries will be provided:

- A summary of the number and percentage of total deaths, deaths related to the disease under investigation (as determined by the investigator), deaths after the end of safety follow-up (28 (±3) days after last dose.
- A summary of the number and percentage of subjects reporting a treatment-emergent SAE by SOC and PT.
- A summary of the number of treatment-emergent SAEs by treatment group, SOC and PT.
- A summary of the number and percentage of subjects reporting a treatment-emergent SAE leading to discontinuation of study drug by SOC and PT.
- A summary of the number and percentage of subjects with a treatment-emergent SAE with an outcome of death by and PT.
- A summary of the primary cause of death by treatment group and PT.

Adverse events of special interest (AESI) for acalabrutinib include ventricular arrhythmias (e.g., ventricular extrasystoles, ventricular tachycardia, ventricular arrhythmia, ventricular fibrillation). AESI PTs are listed in Section 9.1. These events will be summarized as follows:

- A summary of the number and percentage of subjects reporting an AESI by CTCAE grade, group term and PT.
- A summary of the number and percentage of subjects reporting an AESI possibly related to study drug by group term and PT.
- A summary of the number and percentage of subjects reporting an AESI leading to discontinuation of study drug by SOC and PT.

A list of AESI PTs will also be provided.

Events of clinical interest (ECIs) are provided in Section 9.1. These events will be summarized similarly to AESIs and a list of ECI PTs will be provided.

The following by-subject listings will be presented:

- A by-subject listing of key information for serious adverse events (SAEs).
- A by-subject listing of key information for AESIs and ECIs.
- A by-subject listing of deaths, including the date of death, the primary and secondary cause of death, whether an autopsy was performed and whether the death was related to the disease under study.
- A by-subject listing of key information for SAEs with an outcome of death.

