- A by-subject listing of key information for AEs leading to discontinuation of study treatment.

The following subject narratives will be provided:

- Narratives of SAEs with an outcome of death.
- Narratives of SAEs with an outcome other than death.
- Narratives of discontinuation of investigational product due to AEs.
- Narratives of AESIs.
- Narratives of any other medically-relevant AE that does not fall into the above categories.

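### The Section 9.1 term list for the ventricular arrhythmias AESI contains one non-cardiac preferred term, which would be counted in the arrhythmia group term if programmed as written

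*SAP*

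**What the plan says.** Section 9.1 of the SAP opens its AESI part with the sentence "The following preferred terms for the ventricular arrhythmias AESI include" and a single bullet list. The first seven bullets are torsade de pointes and six terms that begin with the word ventricular (arrhythmia, extrasystoles, fibrillation, flutter, tachyarrhythmia, tachycardia). The eighth and last bullet is "Suspected transmission of an infectious agent via product". No sub-heading or second category separates it from the other seven.

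Section 4.5.1.1 describes the concept in words: "Adverse events of special interest (AESI) for acalabrutinib include ventricular arrhythmias", followed by four examples, all ventricular rhythm events. It then hands the operational definition to the appendix: "AESI PTs are listed in Section 9.1. These events will be summarized as follows". Three AESI tables follow:

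- "A summary of the number and percentage of subjects reporting an AESI by CTCAE grade, group term and PT";
- AESIs possibly related to study drug, by group term and PT;
- AESIs leading to discontinuation of study drug, by SOC and PT.

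The same section also plans a list of the AESI PTs, "A by-subject listing of key information for AESIs and ECIs", and "Narratives of AESIs".

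**The concern.** The sentence that introduces the list makes every bullet below it a ventricular arrhythmia term. The eighth bullet concerns suspected transmission of infection through a product and has no connection with heart rhythm. No other part of the SAP explains why it is there.

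Because Section 4.5.1.1 defines AESIs by reference to this list, the error would carry into output. A programmer who builds the look-up from Section 9.1 would assign the term to ventricular arrhythmias, the only AESI group term the SAP names. Safety is a primary objective, and ventricular arrhythmia is the only AESI described in the analysis section. Its subject count should not depend on a term that does not belong to it.

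**Working it through.** The SAP states no figure for this point, so the check is mainly a comparison of passages.

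**1. The list against its own heading (Section 9.1).** Eight terms are listed. Seven are ventricular rhythm terms and one is not: 8 − 7 = 1 term that does not fit the heading.

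**2. The list against the analysis section (Section 4.5.1.1).** The description there names ventricular arrhythmias only. Its four examples (extrasystoles, tachycardia, arrhythmia, fibrillation) all appear among the seven. Nothing in that section corresponds to the eighth term.

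**3. The list against the event-of-clinical-interest (ECI) table (Section 9.1).** The ECI subcategory for ventricular tachyarrhythmias has five terms, all ventricular rhythm terms. The eighth term is absent, but this is weak evidence. That subcategory also omits ventricular arrhythmia and ventricular extrasystoles (7 − 5 = 2), both of which clearly belong in the AESI list. The conclusion therefore rests on steps 1 and 2.

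**4. Where the term would enter, programmed as written.**

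| Planned AESI output | Classified by | Effect of one event coded to the eighth term |
|---|---|---|
| By CTCAE grade | Group term and PT | Counted in the ventricular arrhythmia group term; PT row shows it separately |
| Possibly related to study drug (if so judged) | Group term and PT | Same |
| Leading to discontinuation (if it did) | SOC and PT | Counted as an AESI, but not under the arrhythmia group term |
| By-subject listing | Subject | Listed as an AESI |
| Narratives | Event | Narrative required; no arrhythmia heading is prescribed |

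The arrhythmia group count is affected in the first two rows only.

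**5. Size, for illustration.** Section 1.3 plans about 20 participants, with at least 16 evaluable. Assume one participant has an event coded to this PT and has no ventricular arrhythmia:

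- denominator 20: 1/20 = 5.0 percentage points added to the group term;
- denominator 16: 1/16 = 6.25, or about 6.3 percentage points.

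The Safety Analysis Set includes everyone who received at least one dose, so 20 is the more natural denominator.

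**6. After correction.** With the eighth term removed, or placed under its own heading, the ventricular arrhythmias list has seven terms, all ventricular rhythm terms.

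**The case against.** The strongest reply is that the term may be deliberate. Section 4.5.1.1 says that AESIs include ventricular arrhythmias, which does not rule out a second AESI, and the list stands under a general AESI title. A sub-heading could have been lost in drafting or when the PDF was read. This stands as an argument against simply deleting the term: if it is a second AESI, deletion would remove its AESI tables and its narrative requirement. It does not rescue the list. On the text at hand the term is assigned to ventricular arrhythmias and has no group term of its own, so either intention calls for a correction.

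A second reply is that little depends on it. All three AESI tables show the PT, a list of AESI PTs is planned, and the safety analysis is descriptive. This also stands, and it limits the point to the group-term count.

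A reader might infer more than the SAP supports:

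- **That the event would be hidden under an arrhythmia heading.** It would not, because the PT appears in every AESI table.
- **That it would be narrated as an arrhythmia.** The SAP asks for narratives of AESIs and sets no arrhythmia heading for them.
- **That the arrhythmia count for discontinuations would be wrong.** That table is by SOC and PT, without group term.
- **That the soft-drink suspension or NG tube makes such a report likely.** Nothing in the SAP links the method of administration to this term.
- **That any contamination report would count.** Only an event coded to this exact PT would.

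**Conclusion.** The point holds as a wrong classification rule with small practical impact. One of the eight terms in the ventricular arrhythmias AESI list is not a ventricular arrhythmia, and Section 4.5.1.1 makes that list operative. If one participant with no ventricular arrhythmia had an event coded to the term, the arrhythmia group term would rise by 5 percentage points at 20 participants in the by-grade table. It would rise by the same amount in the possibly-related table if the event were judged possibly related. With no such event, no table changes.

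This assumes that the look-up is built from Section 9.1 as printed and that no heading was lost before the eighth bullet. The SAP alone does not show whether the term is stray or a separate AESI, and the protocol is not at hand to settle it.

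**What to change.** Before database lock, the sponsor should confirm what was intended and take the term out of the ventricular arrhythmias list in Section 9.1.

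- **If the term is stray:** delete the bullet.
- **If it is meant as a separate AESI:** give it its own AESI heading and group term in Section 9.1, and name it in Section 4.5.1.1, so that its events have their own count.

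The cost is one line of SAP text and the matching look-up entry, plus a phrase in Section 4.5.1.1 in the second case. Doing this beforehand avoids having to reclassify a safety event after the data are seen.

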9.2 Fraction of Inspired Oxygen (FiO2)

For all supplemental oxygen delivery devices, the patient is not just breathing the direct oxygen, but rather is breathing a **combination** of room air plus the oxygen from the supplemental device. Different devices deliver to the patient more or less of a % of what is coming in from the tank.

Fraction of Inspired Oxygen (FiO2) for a nasal canula and a Venturi mask are given in the tables below. For other oxygen delivery systems, such as masks, tents, there is more oxygen that "blows by" or is lost, therefore higher flow rate setting on the oxygen tank are needed to achieve the same FiO2. A tracheostomy would require different calculations as well.

Example: with a **nasal cannula**, we assume that the fraction of oxygen that is inspired (above the normal atmospheric level or 20%) increases by 4% for every additional liter of oxygen flow administered.

For a Nasal Cannula: $FiO2 = (Flow Rate (L/min) \times 0.04) + 0.2$

Oxygen tank FLOW RATE in liters / min	FiO2 Fraction of Inspired Oxygen value
0 (no oxygen, just room air)	0.2
1 L / min	0.24
2 L / min	0.28
3 L / min	0.32
4 L / min	0.36
5 L / min	0.4
6 L / min	0.44

For a Venturi Mask:

Oxygen tank FLOW RATE in liters / min	FiO2 Fraction of Inspired Oxygen value	
< 2 L / min	0.2	
$2 L / min \le Flow Rate < 4 L / min$	0.24	
$4 L / min \le Flow Rate < 6 L / min$	0.28	
$6 L / min \le Flow Rate < 8 L / min$	0.31	
$8 L / min \le Flow Rate < 10 L / min$	0.35	
$10 L / min \le Flow Rate < 15 L / min$	0.4	
\geq 15 L / min	0.6	

9.3 Imputation rules for missing or partial AE on concomitant medication

Imputation rules for missing or partial AE on concomitant medication dates

Form		Imputation	
	Start date		
	Missing		
AE and CM	AE/CM ended before first dose date/ randomization date	Impute 1st January with year being the same year as CM/AE end date	
	AE/CM ended after first dose date/ randomization date	Impute date of first dose	
	Partial		
AE and CM	Missing day	Impute 1 st of the month unless AE/CM start month is the same month as the first dose, then impute date of first dose. Check start date is prior to end date.	
	Missing day and month	Impute 1 st January unless AE/CM start year is the same year as the first dose, then impute date of first dose. Check start date is prior to end date.	
	End date		
	Missing		
AE and CM	CM flag ongoing= yes, no or missing and CM start date is prior, on or after first dose date/ randomization	Impute min (date of death, data cut-off/snapshot date)	
	AE stop date missing		
	Partial		
СМ	Missing day	Impute the last day of the month unless month is the same as month of last dose, then impute date of last dose.	
	Missing day and month	Impute date of last dose + 28 days + 3 days	
	Missing day and month	Impute date of last dose + 28 days + 3 days	

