3.5.2 Prior and Concomitant Medications and Procedures

All therapies (drug and non-drug), including herbal preparations, whether prescribed or over-the-counter, that are used during the study will be recorded on the eCRF. Details include generic and/or brand names of the medications, World Health Organisation Drug Dictionary (WHO-DD) encoding (B3 format), reason for use, route, dose, dosing frequency, and start and end dates. Procedures performed during the study will be recorded on the eCRF and details include the procedure name, WHO-DD encoding (B3 format), reason for the procedure, and start and end dates.

Prior therapies are defined as those taken prior to study treatment with a stop date prior to the first dose of study treatment. Concomitant therapies and procedures are defined as those with a stop date on or after the first dose date of study treatment.

Missing start and stop dates for medications and procedures will be handled using the rules described in Section 4.1.

Medications received prior to or concomitantly will be coded using the WHO Drug Dictionary Anatomical Therapeutic Chemical (ATC) classification codes. Concomitant medications will be summarized for the SAS by ATC classification codes. Subjects with the same concomitant medication/procedure multiple times will be counted once per medication/procedure. A medication/procedure that can be classified into more than one chemical and/or therapeutic subgroup will be presented in each subgroup.

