 - Observations recorded on the date closest to the scheduled assessment day (as long as this is within the visit window) will be used as the scheduled assessment. Any observations recorded outside of the visit window will be considered unscheduled visit observations and will not be included in visit-based summaries at a treatment-group level. If multiple observations are recorded per day for ventilator use, the observations closest to 08:00 will be used as the scheduled assessment. If multiple observations are recorded per day for other assessments, the worst assessment reported will be used as the scheduled assessment.
 - For summaries at a subject level, all values will be included (regardless of whether they appear in a corresponding visit-based summary) when deriving a patient level statistic such as a maximum.

No imputation of values for missing data will be performed except for missing or partial start and end dates for AEs and concomitant medication (CM) (Section 9.3). If the data cut-off/snapshot date or the subject's date of death is prior to the date imputed based on the rules outlined in Section 9.3, then the earliest of these dates will be imputed.

4.2 Analysis Methods for Disposition, Demographic, Baseline Characteristics, Prior and Concomitant Medications/Procedures

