4.4.1 Alive and free of respiratory failure at Day 14 (and 28)

The first efficacy endpoint is the proportion of subjects who are alive and free of respiratory failure at Day 14, where respiratory failure is defined in Section 3.3.1.

The point estimate and its 90% confidence interval (CI; using Wald method with continuity correction) will be calculated and summarized. The difference in the proportion of subjects who are alive and free of respiratory failure at Day 14 with its 90% Cis will be included in this summary. The number and percentage of subjects who experienced respiratory failure but were free of respiratory failure at Day 14 will also be included in above summary.

For those wo have respiratory failure, summary statistics for the number of respiratory failures that occurred will be summarized.

This efficacy endpoint will also be summarized (point estimate and 90% CI Wald method with continuity correction as above) by the following subgroups:

• age (predefined age categories defined in Section 4.2.3)

- sex
- race
- ethnicity
- comorbidities (present vs absent)
- history of substance abuse (former/current/never)
- Concomitant antiviral use (yes vs no)
- Respiratory failure at baseline (with vs without, defined in Section 4.2.3)

The method for handling subjects that withdraw/ are lost to follow up prior to Day 14 is detailed in Section 3.3.1.

Similar analysis will be conducted for Day 28.

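### The year-only stop-date rule for concomitant medication ignores the recorded year, so a drug stopped in a year before dosing is classed as concomitant; the end-date rows also lack a check against the start date

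*SAP*

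**What the plan says.** For a medication stop date with day and month missing, the table in SAP Section 9.3 gives "Impute date of last dose + 28 days + 3 days". With only the day missing it gives "Impute the last day of the month unless month is the same as month of last dose, then impute date of last dose".

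The same table tells the programmer "Check start date is prior to end date", but only in the two rows for partial start dates. Section 4.1 adds one limit for all imputed dates: if death or data cut-off comes before the imputed date, "then the earliest of these dates will be imputed".

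The imputed dates feed the classification. Section 3.5.2 states "Missing start and stop dates for medications and procedures will be handled using the rules described in Section 4.1", and Section 4.1 refers on to Section 9.3. Section 3.5.2 then sets the two classes: "Prior therapies are defined as those taken prior to study treatment with a stop date prior to the first dose of study treatment", and "Concomitant therapies and procedures are defined as those with a stop date on or after the first dose date of study treatment". Section 4.2.4 plans separate summaries for each class.

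**The concern.** An imputation rule should fill in what is unknown and leave alone what was recorded. The year-only rule uses the date of last dose and never looks at the recorded year, so it can overwrite a collected fact. If that year lies before dosing, the drug cannot have overlapped with acalabrutinib, yet its imputed stop falls after first dose and it moves to the wrong table.

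The missing-day rule has a smaller fault. Participants are followed for 28 (±3) days after the last dose, so a drug can start after the last dose within the same month. Its stop is then set to the last-dose date, before it began. The rule also compares month with month and does not mention the year.

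At stake is the accuracy of the medication tables and listings. Antiviral use during the study is a subgroup factor for the Day 14 and Day 28 endpoint in Section 4.4.1, so an effect there is conceivable.

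**Working it through.** **Inputs.** The two stop-date rules are from Section 9.3, the cap at death or cut-off from Section 4.1, the class definitions from Section 3.5.2, and the treatment length of up to 14 days from Section 1.2. The SAP gives no calendar dates, so those below are illustrative. There is no stated figure to reproduce.

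**Rules as formulas.**
- Year only: stop = last dose + 28 + 3 = last dose + 31 days.
- Day missing: stop = last dose if the month is that of the last dose, otherwise the last day of the recorded month.
- Then stop = min(stop, death, cut-off).
- Class: concomitant if stop ≥ first dose, otherwise prior.

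**Applied as written** (month taken as month and year):

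| Case | First dose | Last dose | Drug start | Recorded stop | Imputed stop | Class | Result |
|---|---|---|---|---|---|---|---|
| A | 1 Oct 2020 | 14 Oct 2020 | 1 Mar 2019 | 2019 | 14 Nov 2020 | concomitant | outside recorded year; class wrong |
| A, death on 20 Oct 2020 | 1 Oct 2020 | 14 Oct 2020 | 1 Mar 2019 | 2019 | 20 Oct 2020 | concomitant | cap does not help |
| B | 1 Dec 2020 | 14 Dec 2020 | 5 Dec 2020 | 2020 | 14 Jan 2021 | concomitant | outside recorded year; class right |
| C | 1 Oct 2020 | 14 Oct 2020 | 20 Oct 2020 | Oct 2020 | 14 Oct 2020 | concomitant | 6 days before own start; class unaffected |
| D | 10 Oct 2020 | 23 Oct 2020 | 2 Oct 2020 | Oct 2020 | 23 Oct 2020 | concomitant | possible overlap; conservative |
| E | 1 Oct 2020 | 14 Oct 2020 | 2 Sep 2020 | Sep 2020 | 30 Sep 2020 | prior | correct |

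**How general is case A?** Last dose is never before first dose, so last dose + 31 days is always after first dose. A death or cut-off cap cannot bring the date back before first dose either. No year-only record can therefore be classed as prior. For a 2019 stop year, the imputed date falls after 2019 for every last-dose date in 2020.

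**How general is case B?** 30 November + 31 days = 31 December, still in the year. 1 December + 31 days = 1 January. The overrun occurs for last doses from 1 to 31 December.

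**Why B and C do not change the class.** In B the drug is concomitant at 14 January 2021 and also at 31 December 2020, the last date its record allows. In C the imputed stop is the last dose, which is on or after first dose, so the drug is concomitant either way.

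**Month without year.** If the missing-day rule were coded on calendar month alone, a stop in October 2019 with a last dose on 14 October 2020 would become 14 October 2020, repeating the fault of case A. Month and year together is the natural reading and is used above; the text should say so.

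**The case against.** The strongest reply is that this is a small wording gap whose consequences are easily overstated. Much of that stands.

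- **Only case A misclassifies.** B and C alter a listed date. The SAP plans counts by ATC class and listings, with no summary of medication duration. This stands.
- **Case A may be rare or absent.** Section 3.5.2 speaks of therapies used during the study. Prior therapies are also defined and summarised, so some are collected, but the SAP gives no look-back window. That every year-only stop before the dosing year is misclassified follows from the rule; it says nothing about how many exist.
- **Calling a drug concomitant when in doubt is common conservative practice.** This stands where the recorded month or year overlaps dosing, as in D. It does not cover A, where the record excludes overlap.
- **The table layout may be damaged.** The day-and-month row appears twice and no separate row for partial adverse event stop dates is legible. Nothing here relies on the repeat.

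A reader might infer that the error distorts efficacy by about 10 percentage points in the antiviral subgroups. The SAP does not support that. Section 4.4.1 does not say that the subgroup is derived from imputed stop dates. To move a subject, the misdated drug would have to be that subject's only antiviral. The SAP gives no antiviral split. Assuming 20 subjects divided evenly and 5 of 10 responding, losing one subject gives 5/9 = 55.6% or 4/9 = 44.4%, a shift of 5.6 points. Gaining one gives 6/11 = 54.5% or 5/11 = 45.5%, a shift of 4.5 points. Ten points needs an extreme such as 9/10 to 9/9. Efficacy is also secondary and no p-value is planned.

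**Conclusion.** The point holds in a limited form. The year-only rule disregards the recorded year, nothing else in the SAP corrects it, and a drug stopped in a calendar year before dosing is reported as concomitant. The overrun after a December last dose and the stop before start are genuine date errors confined to listings.

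The effect is on the prior and concomitant medication tables and listings, and possibly, but not demonstrably, on the antiviral subgroup. Its frequency cannot be estimated from the SAP. The primary PK and adverse event endpoints are unaffected. The conclusion assumes that the rules are programmed as written and that some medications with a stop year before dosing are collected.

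It would go too far to infer that all partial stop dates fail (case E is correct) or that every possibly prior drug is wrongly handled (case D is an acceptable convention).

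**What to change.** Amend the end-date rows in Section 9.3:

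- **Day and month missing:** impute last dose + 31 days, but restrict the result to the recorded calendar year: 31 December of that year if the imputed date is later, 1 January of that year if it is earlier. Then apply the Section 4.1 cap at death or cut-off.
- **Day missing:** if both month and year equal those of the last dose, impute the later of last dose and medication start date; otherwise impute the last day of the recorded month.
- **All end-date rows:** the imputed end date must not precede the start date.

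Case A then gives 31 December 2019 and stays prior, B gives 31 December 2020, and C gives 20 October 2020. D and E are unchanged.

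Both limits on the year are needed. A rule that only took the earliest of 31 December and last dose + 31 days would fail for a recorded stop year of 2021 with a last dose on 10 November 2020: it gives 11 December 2020, again outside the recorded year. The wording above gives 1 January 2021, or the start date if that is later.

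The cost is a few lines of SAP text and code, with no new data and no change to trial conduct.
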